6.2 Dosage and Administration

Durvalumab will be given every 4 weeks at 1500 mg IV for total of 12 months/13 doses (refer to Section 5.1.3 and 5.1.4 for the administration and monitoring of administration of durvalumab).

6.3 Durvalumab Dose Modification and Toxicity Management

For adverse events (AEs) that are considered at least partly due to administration of durvalumab, the following dose adjustment guidance may be applied:

- Treat each of the toxicities with maximum supportive care (including holding the agent suspected of causing the toxicity where required).
- If the symptoms promptly resolve with supportive care, consideration should be given to continuing the same dose of durvalumab along with appropriate continuing supportive care. If medically appropriate, dose modifications are permitted for durvalumab (see below).
- All dose modifications should be documented with clear reasoning and documentation of the approach taken.

Clinical Study Protocol

Drug Substance Durvalumab (Medi4736)

Study Number MCC 18788/MCC18788/ESR-15-11326

Edition Number 1.9.4

Date **10/08/2018**

In addition, there are certain circumstances in which durvalumab should be permanently discontinued. These circumstances include but not limited to grade 3 toxicity at least possibly related to durvalumab; and prolonged grade 2 toxicity requiring dose delays for more than 2 weeks or requiring prolonged steroid use will discontinue durvalumab.

Following the first dose of durvalumab, subsequent administration of durvalumab can be modified based on toxicities observed (see Table 1, 2, and 3 in Appendix A). Dose reductions are not permitted.

Based on the mechanism of action of durvalumab leading to T-cell activation and proliferation, there is the possibility of observing immune related Adverse Events (irAEs) during the conduct of this study. Potential irAEs include immune-mediated enterocolitis, dermatitis, hepatitis, and endocrinopathies. Subjects should be monitored for signs and symptoms of irAEs. In the absence of an alternate etiology (e.g., infection or PD) signs or symptoms of enterocolitis, dermatitis, hepatitis, and endocrinopathy should be considered to be immune-related.

Dose modification recommendations and toxicity management guidelines for immune-mediated reactions, for infusion-related reactions, and for non-immune-mediated reactions are detailed in Tables 1, 2, and 3 respectively.

In addition, management guidelines for adverse events of special interest (AESIs) are detailed in Section 10.1.3. All toxicities will be graded according to NCI CTCAE V4.03.

7. RESTRICTIONS DURING THE STUDY AND CONCOMITANT TREATMENT(S)

7.1 Restrictions during the study

Contraception

Females of childbearing potential who are sexually active with a nonsterilized male partner must use 2 methods of effective contraception from screening, and must agree to continue using such precautions for at least 90 days following the last infusion of durvalumab; cessation of birth control after this point should be discussed with a responsible physician. Periodic abstinence, the rhythm method, and the withdrawal method are not acceptable methods of birth control.

- Females of childbearing potential are defined as those who are not surgically sterile (i.e., bilateral tubal ligation, bilateral oophorectomy, or complete hysterectomy) or postmenopausal (defined as 12 months with no menses without an alternative medical cause).
- Subjects must use 2 acceptable methods of effective contraception as described in Table 4.
- Non-sterilized males who are sexually active with a female partner of childbearing potential must use 2 acceptable methods of effective contraception (see Table 4) from Day 1 and for 90 days after receipt of the final dose of investigational product.

Table 4. Effective methods of contraception (two methods must be used)

Barrier Methods	Intrauterine Device Methods	Hormonal Methods
Male condom plus spermicide	Copper T	Implants
Cap plus spermicide	Progesterone T ^a	Hormone shot or injection
Diaphragm plus spermicide	Levonorgestrel-releasing intrauterine system (e.g., Mirena [®]) ^a	Combined pill Minipill Patch

^a This is also considered a hormonal method.

Blood donation

Subjects should not donate blood for at least 90 days following the last infusion of durvalumab.

7.2 Concomitant treatment(s)

7.2.1 Permitted concomitant medications

Investigators may prescribe concomitant medications or treatments (e.g., acetaminophen, diphenhydramine) deemed necessary to provide adequate prophylactic or supportive care except for those medications identified as “excluded” as listed in Section 7.2.2.

7.2.2 Excluded Concomitant Medications

The following medications are considered exclusionary during the study.

1. Any investigational anticancer therapy
2. Any concurrent chemotherapy, radiotherapy (except palliative radiotherapy), immunotherapy, biologic or hormonal therapy for cancer treatment. Concurrent use of hormones for noncancer-related conditions (e.g., insulin for diabetes and hormone replacement therapy) is acceptable. <<NOTE: Local treatment of isolated lesions for palliative intent is acceptable (e.g., by local surgery or radiotherapy)>>
3. Immunosuppressive medications including, but not limited to systemic corticosteroids at doses not exceeding 10 mg/day of prednisone or equivalent, methotrexate, azathioprine, and TNF- α blockers. Use of immunosuppressive medications for the management of investigational product-related AEs or in subjects with contrast allergies is acceptable. In addition, use of inhaled and intranasal corticosteroids is permitted. <>
4. Live attenuated vaccines within 30 days of durvalumab dosing (ie, 30 days prior to the first dose, during treatment with durvalumab and for 30 days post discontinuation of durvalumab. Inactivated vaccines, such as the injectable influenza vaccine, are permitted.

Table 5. Prohibited and Rescue Medications

Rescue/supportive medication/class of drug:	Usage:
Concomitant medications or treatments (eg, acetaminophen or diphenhydramine) deemed necessary by the Investigator to provide adequate prophylactic or supportive care, except for those medications identified as “prohibited” as listed above	To be administered as prescribed by the Investigator
Best supportive care (including antibiotics, nutritional support, growth factor support, correction of metabolic disorders, optimal symptom control, and pain management [including palliative radiotherapy, etc])	Should be used when necessary for all patients

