4.2 Exclusion criteria

Subjects should not enter the study if any of the following exclusion criteria are fulfilled:

1. Muscle invasive (T2 or above) urothelial carcinoma or urothelial carcinoma outside the bladder.
2. Involvement in the planning and/or conduct of the study (applies to both AstraZeneca staff and/or staff at the study site) or previous enrolment in the present study.
3. Participation in another clinical study with an investigational product during the last 4 weeks.
4. Any previous treatment with a PD1 or PD-L1 inhibitor, including durvalumab.
5. History of another primary malignancy except for:
 - Malignancy treated with curative intent and with no known active disease ≥ 3 years before the first dose of study drug and of low potential risk for recurrence.
 - Adequately treated non-melanoma skin cancer or lentigo maligna without evidence of disease.
 - Adequately treated carcinoma in situ without evidence of disease eg, cervical cancer in situ.
6. Receipt of the last dose of anti-cancer therapy (chemotherapy, immunotherapy, endocrine therapy, tyrosine kinase inhibitor, biologic therapy, tumor embolization, monoclonal antibodies, other investigational agent) ≤ 30 days prior to the first dose of study drug and within 6 weeks for nitrosourea, mitomycin C or intravesicle therapy).
7. Mean QT interval corrected for heart rate (QTc) ≥ 470 ms calculated from 3 electrocardiograms (ECGs) using Frediricia's Correction.
8. Current or prior use of immunosuppressive medication within 28 days before the first dose of durvalumab, with the exceptions of intranasal and inhaled corticosteroids or systemic corticosteroids at physiological doses, which are not to exceed 10 mg/day of prednisone, or an equivalent corticosteroid.
9. Any unresolved toxicity (CTCAE grade 2 or above) from previous anti-cancer therapy.
<<Subjects with irreversible toxicity that is not reasonably expected to be exacerbated by the investigational product may be included (e.g., hearing loss, peripherally neuropathy)>>

10. Any prior Grade ≥ 3 immune-related adverse event (irAE) while receiving any previous immunotherapy agent, or any unresolved irAE $>$ Grade 1.
11. Active or prior documented autoimmune disease within the past 2 years
NOTE: Subjects with vitiligo, Grave's disease, or psoriasis not requiring systemic treatment (within the past 2 years) are not excluded.
12. Active or prior documented inflammatory bowel disease (e.g., Crohn's disease, ulcerative colitis).

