
Drug administration modifications of study drug/study regimen will be made to manage potential immune-related AEs based on severity of treatment-emergent toxicities graded per NCI CTCAE v4.03.
 
In addition to the criteria for permanent discontinuation of study drug/study regimen based on CTC grade/severity (table below), permanently discontinue study drug/study regimen for the following conditions:
 
• Inability to reduce corticosteroid to a dose of ≤ 10 mg of prednisone per day (or equivalent) within 12 weeks after last dose of study drug/study regimen• Recurrence of a previously experienced Grade 3 treatment-related AE following resumption of dosing 
Grade 1 No dose modification
 
Grade 2 Hold study drug/study regimen dose until Grade 2 resolution to Grade ≤ 1. If toxicity worsens, then treat as Grade 3 or Grade 4. Study drug/study regimen can be resumed once event stabilizes to Grade ≤ 1 after completion of steroid taper. Patients with endocrinopathies who may require prolonged or continued steroid replacement can be retreated with study drug/study regimen on the following conditions:
1. The event stabilizes and is controlled.2. The patient is clinically stable as per Investigator or treating physician's clinical judgement.3. Doses of prednisone are at ≤ 10 mg/day or equivalent.
 
Grade 3 Depending on the individual toxicity, study drug/study regimen may be permanently
	
It is recommended that management of immune-mediated adverse events (imAEs) follows the guidelines presented in this table:
 
– It is possible that events with an inflammatory or immune mediated mechanism could occur in nearly all organs, some of them not noted specifically in these guidelines.– Whether specific immune-mediated events (and/or laboratory indicators of such events) are noted in these guidelines or not, patients should be thoroughly evaluated to rule out any alternative etiology (e.g., disease progression, concomitant medications, and infections) to a possible immune-mediated event. In the absence of a clear alternative etiology, all such events should be managed as if they were immune related. General recommendations follow.– Symptomatic and topical therapy should be considered for low-grade (Grade 1 or 2, unless otherwise specified) events.– For persistent (>3 to 5 days) low-grade (Grade 2) or severe (Grade ≥ 3) events, promptly start prednisone 1 to 2 mg/kg/day PO or IV equivalent.– Some events with high likelihood for morbidity and/or mortality – e.g., myo-carditis, or other similar events even if they are not currently noted in the guidelines – should progress rapidly to high dose IV corticosteroids (methylprednisolone at 2 to 4 mg/kg/day) even if the event is Grade 2, and if clinical suspicion is high and/or there has been clinical confirmation. Consider, as necessary, discussing with the study physician, and promptly pursue specialist consultation.– If symptoms recur or worsen during corticosteroid tapering (28 days of taper), increase the corticosteroid dose (prednisone dose [e.g., up to 2 to 4 mg/kg/day PO or IV equivalent]) until stabilization or improvement of symptoms, then resume corticosteroid tapering at a slower rate (>28 days of taper).– More potent immunosuppressives such as TNF inhibitors (e.g., infliximab) (also refer to the individual sections of the imAEs for specific type of immunosuppressive) should be considered for events not responding to systemic steroids.

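### Section 7.2.2 names systemic corticosteroids at or below 10 mg/day as prohibited on study, the same range that exclusion 8 permits at entry

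*Combined protocol and SAP*

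**What the plan says.** Section 7.2.2 opens with "The following medications are considered exclusionary during the study". Its item 3 covers immunosuppressive medications as a class and gives, as the first in an open-ended list of examples, "systemic corticosteroids at doses not exceeding 10 mg/day of prednisone or equivalent", followed by methotrexate, azathioprine and TNF-α blockers.

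Exclusion criterion 8 has the same wording in the synopsis and in Section 4.2. It bars immunosuppressive medication in the 28 days before the first dose, but excepts intranasal and inhaled steroids and "systemic corticosteroids at physiological doses, which are not to exceed 10 mg/day of prednisone, or an equivalent corticosteroid".

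Section 7.2.1 gives the 7.2.2 list its force. Investigators may give treatments "deemed necessary to provide adequate prophylactic or supportive care except for those medications identified as" excluded in 7.2.2, and Table 5 repeats that carve-out.

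Item 3 has its own exemptions. One is "Use of immunosuppressive medications for the management of investigational product-related AEs or in subjects with contrast allergies is acceptable". It also permits inhaled and intranasal steroids, and a temporary course for various indications at the principal investigator's discretion. Item 2 of the same section accepts hormones for conditions other than cancer, including hormone replacement.

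**The concern.** The same dose range is acceptable under the eligibility criteria and named as prohibited under the concomitant-medication rules. A site that enrolls a subject on a continuing low dose under exclusion 8, and then reads 7.2.2 literally, must either stop a drug that eligibility accepted or record a deviation from the first day. A site that reads for intent would do neither. With 2-3 centers planned, the same prescription could be handled and coded in two ways. Deviations are monitored under Section 14 and reviewed by the protocol monitoring committee under Section 13.2, so the coding is not idle.

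The section also gives no numerical ceiling for on-study use, in a trial of an immunotherapy where systemic steroids are a relevant concomitant drug.

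**Working it through.** No sample size, error rate or event count is involved, so the check is a comparison of texts.

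**Step 1: apply each rule literally.** Take continuing systemic prednisone outside every exemption. The three doses are illustrative assumptions.

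| Dose | Exclusion 8 (entry) | 7.2.2 item 3 as written (on study) | 7.2.2 item 3 with *exceeding* |
|---|---|---|---|
| 5 mg/day | Permitted if physiological (5 ≤ 10) | Named as prohibited (5 ≤ 10) | Not named (5 is not > 10) |
| 10 mg/day | Permitted if physiological (10 ≤ 10) | Named as prohibited (10 ≤ 10) | Not named (10 is not > 10) |
| 15 mg/day | Barred (15 > 10) | Outside the named range; reached only by the open-ended class wording | Named as prohibited (15 > 10) |

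As written, the two rules disagree at 5 and 10 mg/day, and at 15 mg/day they agree only through the general class wording. With *exceeding*, the named range matches exclusion 8 at all three doses.

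**Step 2: could a stricter on-study rule be intended?** A complete ban on systemic steroids would need no dose qualifier, and none is attached to methotrexate, azathioprine or the TNF-α blockers in the same sentence. A threshold ban would name the doses above the threshold. Naming only the lower range serves neither purpose.

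**Step 3: look for the intended direction elsewhere.** The general considerations in Appendix A require permanent discontinuation for "Inability to reduce corticosteroid to a dose of ≤ 10 mg of prednisone per day (or equivalent) within 12 weeks" of the last dose. Appendix A also lets subjects with endocrinopathy on continued steroid replacement be retreated if prednisone is at or below 10 mg/day. This is not a second conflict, because item 3 exempts steroids given for drug-related adverse events. It does show that 10 mg/day is meant as the upper limit of acceptable use.

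**Step 4: trace the consequences.**
- None of the nine discontinuation triggers in Section 4.3 names use of a prohibited medication. Trigger 2 mentions prolonged steroid use, but as part of an adverse-event criterion, and Section 6.3 ties it to toxicity. Trigger 7 (noncompliance) is a matter of judgment.
- The efficacy set in Section 11.1.2 requires at least 6 infusions and the month 6 mapping biopsy. It has no concomitant-medication condition.
- Withdrawal, replacement, the evaluable count and the two-stage rule (13 then 34 subjects, cut-offs 3 and 9) therefore do not depend on how item 3 is read.

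**The case against.** The strongest reply is that this is a slip with almost no reach.

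- **Direction of the error.** Item 3 bans immunosuppressants as a class and gives examples, so doses above 10 mg/day are still prohibited. Read literally, the rule is too strict; it does not license immunosuppressive doses. This stands, and the missing numerical ceiling is a weakness of clarity, not a gap in the ban.
- **Who is affected.** Exclusions 11 (autoimmune disease, with narrow exceptions), 12 (inflammatory bowel disease), 14 (allogeneic transplant) and 15 (pneumonitis) remove several common reasons for long-term low-dose prednisone. True replacement therapy arguably falls under the hormone exemption in item 2. Temporary courses are exempt, with chronic obstructive pulmonary disease as a named example. This also stands: the remaining group is small and may be empty.
- **Different periods.** Exclusion 8 governs the 28 days before the first dose, and 7.2.2 governs the study itself, so a tighter on-study rule is not contradictory in principle. This carries less weight. Nothing in the protocol says that a subject admitted on low-dose steroids must stop them at Day 1, and a ban that names only the low range is not a coherent tightening.
- **Intent is recoverable.** A careful reader can infer the meaning from exclusion 8 and Appendix A. That is fair, but 7.2.2 is the operative rule and no sentence elsewhere corrects it. That centers would actually diverge is a possibility, not something the documents show.

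**Conclusion.** The concern holds. Item 3 of Section 7.2.2 is wrong as written: it names as prohibited the steroid range that exclusion 8 permits, and Appendix A supports the opposite direction. Severity is minor. The practical effect is confined to subjects on continuing systemic steroids at or below 10 mg/day who are not otherwise excluded and who fall outside the exemptions for drug-related adverse events, contrast allergy, temporary use and hormone replacement. The documents give no count of them. The consequence is inconsistent handling or deviation coding, or a site stopping a drug that eligibility accepted. There is no effect on the design, the stated type I error of 0.047, the 80% power or the evaluable set. That *exceeding* was intended is an inference from the other sections, though a strong one.

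**What to change.** In item 3 of Section 7.2.2, replace *not exceeding* with *exceeding*, so that the named range is above 10 mg/day of prednisone or equivalent. Add a sentence stating that physiological systemic doses of 10 mg/day or less remain permitted on study, as in exclusion 8. Leave the existing exemptions as they are. This also supplies the explicit on-study ceiling that the section lacks. The cost is a one-line wording amendment that can go into the next protocol revision, with no change to endpoint, sample size or analysis.

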8. STUDY PROCEDURES

8.1 Schedule of study procedures

Before study entry, throughout the study, and following study drug discontinuation, various clinical and diagnostic laboratory evaluations are outlined. The purpose of obtaining these detailed measurements is to ensure adequate safety and tolerability assessments. Clinical evaluations and laboratory studies may be repeated more frequently if clinically indicated. The Schedules of Assessments during the screening and treatment period is provided following the Protocol Synopsis (*note that these are the minimum requirements and the table will be adjusted according to each individual study*).

8.1.1 Screening Phase

Subjects with BCG refractory CIS urothelial bladder cancer will be consented and then screened for the study. Screening procedures will be performed up to 28 days before Day 1 Cycle 1, unless otherwise specified. All subjects must first read, understand, and sign the IRB/REB/IEC-approved ICF before any study-specific screening procedures are performed. After signing the ICF, completing all screening procedures, and being deemed eligible for entry, subjects will be enrolled in the study. Procedures that are performed prior to the signing of the ICF and are considered standard of care may be used as screening assessments if they fall within the 28-day screening window.

The following procedures will be performed during the Screening Visit:

- Informed Consent
- Review of eligibility criteria
- Medical history and demographics
- Complete physical exam
- ECOG Performance Status
- Vitals signs, weight and height
- 12-lead ECG (in triplicate [2-5 minutes apart])
- Review of prior/concomitant medications
- CT urogram and chest X-ray to rule out metastasis
- Clinical laboratory tests for:
 - Hematology (see Table 6)
 - Clinical chemistry (see Table 7)
 - TSH
 - Coagulation (PT, PTT, INR)
 - Creatinine Clearance
 - Serum pregnancy test (for women of childbearing potential only)
 - Hepatitis serologies
 - Urinalysis (see Table 8)
 - Urine cytology with Urovysion FISH test

8.1.2 Treatment Phase

Procedures to be conducted during the treatment phase of the study are presented in the Schedule of Assessments. Screening procedures performed within 72 hours of Cycle 1 Day 1 (C1D1) do not need to be repeated on C1D1.

8.1.3 End of Treatment

End of treatment is defined as the last planned dosing visit within the 12-month dosing period. For subjects who discontinue durvalumab prior to 12 months, end of treatment is considered the last visit where the decision is made to discontinue treatment. All required procedures may be completed within \pm 7 days of the end of treatment visit. <<Repeat disease assessment is not required if performed within 28 days prior to the end of treatment visit.>>

Assessments for subjects who have completed durvalumab treatment and achieved disease control, or have discontinued durvalumab due to toxicity in the absence of confirmed progressive disease are provided in APPENDIX C.

Assessments for subjects who have discontinued durvalumab treatment due to confirmed PD are presented in APPENDIX D.

8.2 Description of study procedures

8.2.1 Medical history and physical examination, electrocardiogram, weight and vital signs

Findings from medical history (obtained at screening) and physical examination shall be given a baseline grade according to the procedure for AEs. Increases in severity of pre-existing conditions during the study will be considered AEs, with resolution occurring when the grade returns to the pre-study grade or below.

Physical examinations will be performed on study days noted in the Schedule of Assessments.

A complete physical examination will be performed and will include an assessment of the following (as clinically indicated): general appearance, respiratory, cardiovascular, abdomen, skin, head and neck (including ears, eyes, nose and throat), lymph nodes, thyroid, musculoskeletal (including spine and extremities), genital/rectal, and neurological systems and at screening only, height.

ECGs are required during screening as well as at any other time point when clinically indicated. ECGs recorded during the screening period will be obtained in triplicate (with 2-5 minute lag time between each). All 12-lead ECGs should be recorded while the subject is in the supine position for at least 5 minutes in each case.

Vital signs (temperature, blood pressure, pulse rate, and respiratory rate) will be measured on study days noted in the Schedule of Assessments. On durvalumab treatment days, vital signs will be measured within an hour prior to start of durvalumab administration, at 30 minutes during the infusion (\pm 5 minutes), at the end of infusion (+ 5 minutes), and at 30 minutes (\pm 5 minutes) and 60 minutes (\pm 5 minutes) post-infusion. If the infusion takes longer than 60 minutes, then blood pressure and pulse measurements should follow the principles described here, or more frequently if clinically indicated. For subsequent doses, the 1-hour observation period will not be required unless a subject experiences an infusion-related reaction.

